#### 9.4.2. Follow-up information

The follow-up information will be collected at immunisation visits, at telephone follow-up contacts defined in the protocol and through spontaneous reporting by the patient or his LAR or a physician. This will include information about:

- concomitant medication/vaccination
- occurrence of medically attended AEFI occurring during the 30 days following each immunisation with *Cervarix*
- occurrence of serious AEFI during the period starting at the first immunisation and ending either 12 months following the third immunisation or 24 months following the first immunisation with *Cervarix* (whichever occurs first).
- occurrence of pIMD during the period starting at the first immunisation and ending either 12 months following the third immunisation or 24 months following the first immunisation with *Cervarix* (whichever occurs first).
- exposure to *Cervarix* during pregnancy or pregnancy onset within 60 days following any immunisation, as well as the related PO and presence of congenital anomalies.

#### 9.4.3. Safety events

All events described under section 9.3, exposure to *Cervarix* during pregnancy or pregnancy onset within 60 days following any immunisation, as well as the related PO and presence of congenital anomalies are described as safety events.

### 9.5. Study size

#### 9.5.1. Overall sample size estimation

As per the Chinese regulation requirement, safety information will be collected from approximately 3000 subjects for the PMS study [3000 subjects is the minimum target for the Exposed Set (ES)].

Table 4 presents the exact two-sided 95% CI of the proportion of subjects reporting medically attended AEFI for a sample size of 3000 subjects. The percentage of subjects reporting at least one medically significant AE was 6.1% [95% CI; 5.3%-7.1%] during a follow-up period of 72 months in the efficacy clinical trial conducted in China [Zhu, 2014]. The follow-up of the medically attended AEFI for this study will be 30 days after each dose of the vaccination, therefore 90 days in total after 3 doses of the vaccination. Under a conservative assumption of constant incidence of AE's during the 72 months of follow-up period, the percentage of subjects reporting at least one medically attended AEFI during the 90-day follow-up period of this study is assumed to be 0.25%. Since decreasing incidence rate with time from vaccination is plausible, a range of percentage from 0.20 to 1.0% is presented in Table 4.

**Table 4** Exact two-sided 95 percent CI for a sample size of 3000 according to different proportion of subjects reporting medically attended AEFI 30 days after each dose of vaccination

Proportion (number of subjects reporting at least one medically attended AE or SAE)	Exact two-sided 95% CI	
	Lower limit (LL)	Upper limit (UL)
0.20% (6)	0.07%	0.43%
0.25% (7.5)	0.10%	0.50%
0.30% (9)	0.14%	0.57%
0.35% (10.5)	0.17%	0.63%
0.50% (15)	0.28%	0.82%
1.00% (30)	0.68%	1.42%

Table 5 presents the exact two-sided 95% CI of the proportion of subjects reporting serious AEFI for a sample size of 3000 subjects. The percentage of subjects reporting at least one SAE was 1.9% [95% CI; 1.4%-2.4%] during a follow-up period of 72 months in the efficacy clinical trial conducted in China [Zhu, 2014]. The follow up of serious AEFI for this study will be at least 18 months after the first dose of vaccination for a subject completing the full vaccination course (three doses). Therefore, the percentage of subjects reporting serious AEFI is assumed to be 0.5%.

**Table 5** Exact two-sided 95 percent CI for a sample size of 3000 according to different proportion of subjects reporting serious AEFIs

Proportion (number of subjects reporting at least one medically attended AE or SAE)	Exact two-sided 95% CI	
	Lower limit (LL)	Upper limit (UL)
0.50% (15)	0.28%	0.82%
1.00% (30)	0.68%	1.42%
1.50% (45)	1.10%	2.00%
2.00% (60)	1.53%	2.57%

## 9.6. Data management

A validated GSK defined electronic data collection tool will be used as the method for data collection.

Adverse events and concomitant medications terms will be coded using medical dictionary for regulatory activities (MedDRA) and validated medication dictionary, such as GSK drug dictionary (GSKDRUG). In all cases, Personally Identifiable Information (PII) will not be collected nor transmitted to GSK (refer to Annex 2 for definition). Subject data necessary for analysis and reporting will be entered into a validated database or data system. Clinical data management will be performed in accordance with applicable GSK standards and data cleaning procedures.

While completed eCRFs are reviewed by a GSK Biologicals' Site Monitor or his/her delegate at the study site, omissions or inconsistencies detected by subsequent eCRF review may necessitate clarification or correction of omissions or inconsistencies with documentation and approval by the investigator or appropriately qualified designee. In all cases, the investigator remains accountable for the study data.

Once the database is archived and the study report is complete and approved by all responsible parties, the participating investigator will be provided with a CD-ROM of the final version of the data generated from the investigational site.

## **9.7. Data analysis**

All the statistical calculations will be done in SAS 9.2 or higher.

## **9.8. Analysis set**

### **9.8.1. Exposed Set**

The ES will include all subjects exposed to *Cervarix*.

## **9.9. Statistical analyses**

### **9.9.1. Analysis of demographics/baseline characteristics**

The mean age (plus range and standard deviation) and race of the enrolled subjects, will be calculated.

The vaccination history of the vaccinated subjects will be also presented.

The distribution of subjects enrolled in different centres will be tabulated.

### **9.9.2. Analysis for Primary endpoint**

The analysis will be based on the ES.

The percentage of subjects with at least one medically attended AEFI occurring within the 30-day (Day 1-30) follow-up period will be tabulated with exact 95% CI after each vaccine dose and overall per dose.

The same tabulation will be performed for medically attended AEFI causally related to vaccination occurring within the 30-day (Day 1-30) follow-up period.

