- Vaccination schedule: Chinese female subjects aged between 9 and **45** years, who consented to participate in the study, are expected to receive three doses of *Cervarix* at 0, 1 and 6 months. The second dose can be administered between 1 month and 2.5 months after the first dose and the third dose between 5 and 12 months after the first dose. The vaccine will be administered intra-muscularly, in the deltoid region of the upper arm.

*Note: Cervarix will be available for purchase at immunisation centres or Point of Vaccination (POV).*

- Data collection: electronic Case Report form (eCRF) will be used to collect data.
- Study duration: The follow-up will be performed from enrolment until either 12 months following the third immunisation or 24 months following the first immunisation with *Cervarix* (whichever occurs first). This represents an individual subjects' total follow-up time between 18 and 24 months for subjects completing the immunisation course (3 doses) as per *Cervarix* PI schedule. Subjects who report exposure to *Cervarix* during pregnancy or pregnancy onset up to 60 days following the last immunisation will be followed-up till end of pregnancy, to observe the PO and for any possible congenital anomalies diagnosed during the first 12 months of the child's life. Thus, in such cases, an extended follow-up beyond 24 months may occur.
- Epoch 001: Prospective data collection (for each subject) starting at Visit 1 (Day 1) and ending either 12 months following the third immunisation or 24 months following the first immunisation with *Cervarix*, whichever occurs first.

The study cohorts and epoch foreseen in the study are presented in [Table 1](#).

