### **9.9.3. Analysis for Secondary endpoints**

The occurrence of serious AEFIs will be assessed throughout the entire follow-up period in all enrolled subjects. Serious AEFIs will be further evaluated for their clinical relevance and relationship to vaccination.

The occurrence of pIMD(s) will be collected and summarized through the entire follow-up period in all enrolled subjects.

The PO and congenital anomalies will be summarized when *Cervarix* is administered within 60 days before pregnancy onset or any time during pregnancy. In addition, the PO

will be summarized by the time of the vaccination, such as vaccination before the pregnancy, vaccination during the first trimester of the pregnancy, vaccination during the second trimester of the pregnancy etc.

All secondary endpoints (serious AEFIs, pIMDs and POs) will be summarized by percentage of subjects reporting the endpoint with exact 95% CI.

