5.4. Analysis of safety and reactogenicity**5.4.1. Analysis for Primary endpoint**

The analysis will be based on the ES.

The percentage of subjects with at least one medically attended AEFI occurring within the 30-day (Day 1-30) follow-up period will be tabulated with exact 95% CI after each vaccine dose and overall. The tabulation will be done using the MedDRA classification of System Organ Class and Preferred term.

The same tabulation will be performed for medically attended AEFI causally related to vaccination occurring within the 30-day (Day 1-30) follow-up period.

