5.4.2. Analysis for Secondary endpoints

The analysis will be based on the ES.

The occurrence of serious AEFIs will be assessed throughout the entire follow-up period. Serious AEFIs will be further evaluated for their clinical relevance and relationship to vaccination.

The percentage of subjects with serious AEFI occurring within the 30-day (Day 1-30) follow-up period will be tabulated with exact 95% CI after any dose.

The occurrence of pIMD(s) will be collected and summarized through the entire follow-up period in all exposed subjects.

The PO and congenital anomalies will be summarized when *Cervarix* is administered within 60 days before pregnancy onset or any time during pregnancy. In addition, the PO will be summarized by the time of the vaccination, such as vaccination before the pregnancy, vaccination during the first trimester (LMP through week 13) of the pregnancy, vaccination during the second trimester (week 14 through week 27) of the pregnancy, vaccination during the third trimester (week 28 through term) of the pregnancy.

All secondary endpoints (serious AEFIs, pIMDs and POs) will be summarized by percentage of subjects reporting the endpoint with exact 95% CI.

CONFIDENTIAL207350 (EPI-HPV-070 VS CN PMS)
Statistical Analysis Plan**5.4.3. Additional considerations**

The percentage of subjects with at least one medically attended non-serious AEFI occurring within the 30-day (Day 1-30) follow-up period will be tabulated with exact 95% CI after any dose.

The percentage of subjects, who have used any medications, that was required to be reported as per protocol, during the whole study period will be tabulated. Medications will be coded using the GSKDRUG dictionary.

All primary and secondary endpoints (medically attended AEFIs, serious AEFIs, , casually related AEFIs , grade 3 AEFIs, pIMDs and POs) will be summarized by percentage of subjects and percentage of doses reporting the symptoms with exact 95% CI.

Incidence and nature of reported AEFIs following each dose and overall will be presented. The analysis will be done for any AEFI, medically attended AEFI within 30 days follow-up period and serious AEFI.

Adverse events will be coded using medical dictionary for regulatory activities - MedDRA classification of System Organ Class and Preferred term.

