10.1.1. Attributing events to vaccine doses

The dose relative to an event is the most recent study dose given to a subject prior to the start of a given event. For example, if the start date of an adverse event is between Dose 1 and Dose 2, the relative dose will be Dose 1.

If an event starts on the same day as a study dose, the relative dose will be derived from the additional information provided in the CRF using the contents of the flag indicating if the event occurred before or after vaccination. If 'after vaccination' is selected, the relative dose for the event will be the one administered on the start day of the event. If 'before vaccination' is selected, the relative dose for the event will be the dose prior to this one.

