10.1.5. Statistical methodology**10.1.5.1. Exact confidence intervals around proportions**

The exact confidence intervals around within-group proportions are derived using the method of Clopper and Pearson [[Clopper](#), 1934].

CONFIDENTIAL207350 (EPI-HPV-070 VS CN PMS)
Statistical Analysis Plan

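### The SAP's percentage of doses is the wrong unit for serious AEFIs, pIMDs and pregnancy outcomes, and for 30-day events its exact interval ignores repeat doses in one woman

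*Protocol*

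**What the plan says.** For the primary endpoint, Protocol 9.9.2 starts from the percentage of subjects with an event and says it "will be tabulated with exact 95% CI after each vaccine dose and overall per dose". SAP 5.4.1 repeats the plan without the last two words: "will be tabulated with exact 95% CI after each vaccine dose and overall".

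For the secondary endpoints, Protocol 9.9.3 names one unit, the subject: serious AEFIs, pIMDs and pregnancy outcomes "will be summarized by percentage of subjects reporting the endpoint with exact 95% CI". SAP 5.4.2 keeps that statement. SAP 5.4.3, under additional considerations, then says that all primary and secondary endpoints, naming these three, "will be summarized by percentage of subjects and percentage of doses reporting the symptoms with exact 95% CI". It also asks for incidence following each dose and includes serious AEFIs there without a time limit.

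Three other rules matter:
- SAP 10.1.1, on attribution: "The dose relative to an event is the most recent study dose given to a subject prior to the start of a given event". It sets no upper limit on the interval.
- SAP 10.1.5.1, on intervals: "The exact confidence intervals around within-group proportions are derived using the method of Clopper and Pearson". No clustering term is given, and SAP section 9 declares no non-standard methods.
- SAP section 8 lists one departure from the protocol, the use of the Exposed Set. The added dose denominator is not there.

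**The concern.** There are two separate problems.

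The first concerns what a dose percentage means for a whole-period endpoint. Serious AEFIs and pIMDs are followed until 12 months after dose 3 or 24 months after dose 1, whichever comes first. Under the attribution rule each dose then owns a stretch of follow-up of a different length. A by-dose display would mostly reflect those lengths, and a flat event rate would look like a rise with each dose. The pooled dose percentage also spreads one long observation period per woman over up to three denominators, which makes the risk look smaller. For pregnancy outcomes, a denominator of all doses given includes doses with no pregnancy exposure.

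The second concerns the 30-day medically attended AEFIs. There the windows are comparable, but Clopper-Pearson assumes independent units. If the same women tend to have events after more than one dose, an interval on doses is too narrow. The study is descriptive, so its estimates and intervals are its main product.

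**Working it through.** **Inputs.** Protocol 9.5.1: "3000 subjects is the minimum target for the Exposed Set (ES"). Protocol 9.1: women "who consented to participate in the study, are expected to receive three doses of" the vaccine, at 0, 1 and 6 months, with dose 2 allowed at 1 to 2.5 months and dose 3 at 5 to 12 months. Planned rates (Protocol 9.5.1): medically attended AEFI 0.25% of subjects, range 0.20 to 1.0%; serious AEFI 0.5% (15 women). Assumptions: every woman receives three doses (9000 doses), and the dose denominator, which the SAP does not define, is all doses given.

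**The plan's own figures.** Clopper-Pearson limits are Beta(0.025; x, n−x+1) and Beta(0.975; x+1, n−x). With n = 3000 they reproduce every row of Protocol Tables 4 and 5 to two decimals; for example 15/3000 gives 0.28 to 0.82%.

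**Whole-period endpoints: windows by dose.**
- Doses at 0, 1, 6 months, end at month 6 + 12 = 18: windows 1, 5 and 12 months.
- Doses at 0, 2.5, 12 months, end at month 24: windows 2.5, 9.5 and 12 months.
- Doses at 0, 1, 12 months, end at month 24: windows 1, 11 and 12 months.
- A woman who stops after dose 1 puts up to 24 months on dose 1. One who stops after a dose 2 at month 1 puts up to 23 months on dose 2.

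With 15 serious AEFIs at a constant rate on the 0, 1, 6 schedule, the expected split is 15×1/18 = 0.8, 15×5/18 = 4.2 and 15×12/18 = 10. Over 3000 women per dose that is 0.03%, 0.14% and 0.33%: an apparent rise with no change in risk.

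**Whole-period endpoints: pooled figure.** By subject, 15/3000 = 0.50% (0.28 to 0.82%). By dose, counting each woman once, 15/9000 = 0.17% (0.09 to 0.27%). The estimate falls threefold, and the dose interval excludes the subject-level 0.50%.

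**30-day events: coverage.** With three doses per woman and within-woman correlation rho, the design effect is 1 + 2·rho. The documents give no rho, so a range is assumed. Coverage of the unadjusted 9000-dose interval was computed from the exact distribution of the total over 3000 beta-binomial clusters of size 3. Per-dose rates are 0.25%/3 = 0.083% and 1.0%/3 = 0.33%, with 1% added as a rate above the planned range.

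| rho | 0.083% | 0.33% | 1% |
|---|---|---|---|
| 0 | 95.8% | 95.6% | 95.6% |
| 0.02 | 95.4% | 95.2% | 95.2% |
| 0.05 | 94.8% | 94.6% | 94.5% |
| 0.1 | 93.7% | 93.5% | 93.4% |
| 0.3 | 89.2% | 88.9% | 88.9% |

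At these rates rho is close to the share of affected women with events after two or more doses: about 10% at rho 0.1 and 28% at rho 0.3.

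**30-day events: displayed limits.** SAP 10.1.4.1 shows confidence limits to one decimal. Using an effective number of doses of 9000/(1 + 2·rho), 30 events give 0.225 to 0.476% at rho 0 and 0.200 to 0.522% at rho 0.3; both display as 0.2 to 0.5%. Across the Table 4 counts (6 to 30) and rho up to 0.3, a displayed limit changes only at 6 and 10.5 events, by 0.1 point.

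**The case against.** The strongest reply is that dose percentages are a supplementary display. The Protocol 9.9.2 sentence is about subjects, and SAP 5.4.1 drops the per-dose wording, so its overall figure reads naturally as one observation per woman. Secondary endpoints are also reported by subject. No test or error rate depends on any of this. All of that stands.

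A reader might infer from Protocol 9.9.2 that the study's main primary result loses its 95% coverage. The documents do not support that. The interval is too narrow only if events recur materially in the same women, and no document says how often they do. Clopper-Pearson is conservative, which absorbs a correlation of about 0.02. At the planned 0.25% (7.5 women), rho 0.1 means about one affected woman with events after two or more doses, and rho 0.3 about two. Missed doses would shrink the clusters.

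A reader might also apply the 1, 5, 12 month pattern to pregnancy outcomes, or take it as fixed. Neither is right. Pregnancies count only with vaccination during pregnancy or in the 60 days before onset, so their problem is the denominator. For serious AEFIs and pIMDs the split varies with dose timing and early stopping.

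The reply does not rescue the whole-period display. That problem needs no assumed correlation, and reporting subjects alongside does not make the dose figure interpretable.

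**Conclusion.** The point holds in two parts of different weight.

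The main part is the dose percentage in SAP 5.4.3 for serious AEFIs, pIMDs and pregnancy outcomes. It departs from Protocol 9.9.3 without being listed as a change. For serious AEFIs and pIMDs it compares unequal windows and dilutes the pooled risk up to threefold if all women receive three doses. For pregnancy outcomes it counts unexposed doses, if the denominator is all doses given.

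The second part is conditional. The dose-level exact interval for 30-day events has no allowance for repeated doses. The loss of coverage is negligible at rho 0.02, small at 0.05, about 1.5 points at 0.1 and about 6 points at 0.3. Within the planned rates it hardly shows at the reported precision; the limits would move more if events proved more frequent. Intervals by subject, whether after each dose or overall, and Protocol Tables 4 and 5 are unaffected.

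**What to change.** - In SAP 5.4.3, drop the percentage of doses for serious AEFIs, pIMDs and pregnancy outcomes. Report the first two by subject, and pregnancy outcomes also by exposed pregnancy.
- In SAP 5.4.1, state that the overall figure is per subject. This settles the difference from Protocol 9.9.2.
- If the dose percentage is kept for 30-day medically attended AEFIs, give it an interval clustered by subject (for example a subject-level bootstrap or a cluster-robust interval), or show counts without an interval.
- Record the change of unit in SAP section 8.

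The cost is SAP wording and a few lines of code. Any dose-level interval that is kept becomes slightly wider. No new data are needed.

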### **9.9.3. Analysis for Secondary endpoints**

The occurrence of serious AEFIs will be assessed throughout the entire follow-up period in all enrolled subjects. Serious AEFIs will be further evaluated for their clinical relevance and relationship to vaccination.

The occurrence of pIMD(s) will be collected and summarized through the entire follow-up period in all enrolled subjects.

The PO and congenital anomalies will be summarized when *Cervarix* is administered within 60 days before pregnancy onset or any time during pregnancy. In addition, the PO

will be summarized by the time of the vaccination, such as vaccination before the pregnancy, vaccination during the first trimester of the pregnancy, vaccination during the second trimester of the pregnancy etc.

All secondary endpoints (serious AEFIs, pIMDs and POs) will be summarized by percentage of subjects reporting the endpoint with exact 95% CI.

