**9.2.5.2.8. Reporting of serious AEFIs and any pIMDs**

The investigator will record any serious AEFIs or pIMDs reported by the subject or by the physician during any of the immunisation visits or telephone calls. The reporting period will begin from the first immunisation and will end either 12 months following the third immunisation or 24 months following the first immunisation with *Cervarix* (whichever occurs first). A follow-up may be required to collect the relevant medical data. The data collected will be recorded in the eCRF.

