### 9.3.1.4. Potential immune mediated disease (pIMD)

Potential immune mediated diseases (pIMDs) are a subset of AEFIs that include autoimmune diseases and other inflammatory and/or neurologic disorders of interest which may or may not have an autoimmune aetiology. A list is provided in [Table 3](#).

Table 3 List of pIMDs

Neuroinflammatory disorders	Musculoskeletal disorders	Skin disorders

 
• Cranial nerve neuropathy, including paralysis and paresis (e.g. Bell's palsy).
 
• Optic neuritis.
 
• Multiple sclerosis.
 
• Transverse myelitis.
 
• Guillain-Barré syndrome, including Miller Fisher syndrome and other variants.
 
• Acute disseminated encephalomyelitis, including site specific variants e.g.: non-infectious encephalitis, encephalomyelitis, myelitis, myeloradiculoneuritis.
 
• Myasthenia gravis, including Lambert-Eaton myasthenic syndrome.
 
• Demyelinating peripheral neuropathies including:
 
• Chronic inflammatory demyelinating polyneuropathy,
 
• Multifocal motor neuropathy
 
• Polyneuropathies associated with monoclonal gammopathy.
 
• Narcolepsy.
 
	
 
• Systemic lupus erythematosus and associated conditions
 
• Systemic scleroderma (Systemic sclerosis), including:
 
• Diffuse Scleroderma
 
• CREST syndrome
 
• Idiopathic inflammatory myopathies, including:
 
• Dermatomyositis
 
• Polymyositis
 
• Anti-synthetase syndrome.
 
• Rheumatoid Arthritis and associated conditions including:
 
• Juvenile Idiopathic Arthritis
 
• Still's disease.
 
• Polymyalgia rheumatica.
 
• Spondyloarthropathies, including:
 
• Ankylosing Spondylitis,
 
• Reactive Arthritis (Reiter's Syndrome),
 
• Undifferentiated Spondyloarthritis,
 
• Psoriatic Arthritis,
 
• Enteropathic arthritis.
 
• Relapsing Polychondritis.
 
• Mixed Connective Tissue disorder.
 
• Gout.
 
	
 
• Psoriasis.
 
• Vitiligo.
 
• Erythema nodosum.
 
• Autoimmune bullous skin diseases (including pemphigus, pemphigoid and dermatitis herpetiformis).
 
• Lichen planus.
 
• Sweet's syndrome.
 
• Localised Scleroderma (Morphea).
 

Vasculitis	Blood disorders	Others

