### 11.1. Detecting and recording medically attended AEFIs, serious AEFIs, pIMDs and pregnancies

#### 11.1.1. Prompt reporting of medically attended AEFIs, serious AEFIs, pIMDs and pregnancy to GSK Biologicals

Any causally related medically attended AEFIs occurring within 30 days following each immunisation with *Cervarix*, serious AEFIs, pIMDs and pregnancies will be reported promptly to GSK as described in [Table 6](#) once the investigator determines that the event meets the protocol definition.

**Table 6 Time frames for submitting medically attended AEFIs, serious AEFIs, pIMDs and pregnancy reports to GSK Biologicals**

Type of Event	Initial Reports		Follow-up Information on a Previous Report	
	Time Frame	Documents	Time Frame	Documents
Causally related medically attended AEFIs	5 days*	Expedited AEFI screen	5 days*	Expedited AEFI screen
All serious AEFIs	24 hours*	Expedited AEFI screen	24 hours*	Expedited AEFI screen
pIMDs	24 hours*	Expedited AEFI screen	24 hours*	Expedited AEFI screen
Pregnancies	24 hours*	Pregnancy report form	24 hours*	Pregnancy report form

\* Time frame allowed after receipt or awareness of the information.

In case the electronic reporting system is temporarily unavailable, a back-up system is in place. Please refer to Section 11.1.4.1 for a detailed description.

Study Contact for Reporting serious AEFIs	
Please see the Sponsor Information Sheet for contact details of who to contact in the event of a serious AEFI. In addition, the GSK Biologicals Clinical Safety Physician can be contacted in an emergency.	
Back-up study contact for reporting serious AEFIs	
GSK Biologicals Clinical Safety & Pharmacovigilance	
Fax: PPD	/ PPD
China Pharmacovigilance	
Fax: PPD	
Email: PPD	
Back-up e-mail ID	
PPD	
24/24 hour and 7/7 day availability	

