### **11.3. Reporting and follow-up of AEFIs, serious AEFIs, pIMD and pregnancies**

GSK Biologicals has a legal responsibility to promptly notify, as appropriate, both the local regulatory authority and other regulatory agencies and will comply with the Chinese guidelines of National Monitoring Program for Suspected Adverse Event Following Immunisation (AEFI).

- To provide real-time safety information, medically-attended AEFIs, serious AEFIs, pIMDs and pregnancies will be reviewed on a continuous basis by GSK safety physicians.

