9. NON-STANDARD DATA DERIVATION RULES AND STATISTICAL METHODS

Not applicable.

CONFIDENTIAL207350 (EPI-HPV-070 VS CN PMS)
Statistical Analysis Plan

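### The only pIMD identification described is by the site investigator, and the MedDRA-coded AEFIs are not searched against Table 3, so listed diseases recorded only as other AEFIs may be missed from the pIMD endpoint

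*Protocol*

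**What the plan says.** **Definition.** Protocol 9.3.1.4 states: "Potential immune mediated diseases (pIMDs) are a subset of AEFIs that include autoimmune diseases" and other inflammatory or neurologic disorders of interest. Table 3 gives the diseases by name, with no MedDRA preferred terms attached.

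**Capture.** Protocol 9.2.5.2.8 states: "The investigator will record any serious AEFIs or pIMDs reported by the subject or by the physician", at visits or calls. Protocol 11.1.1 has events sent promptly to the sponsor "once the investigator determines that the event meets the protocol definition".

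**Coding.** Protocol 9.6 and SAP 5.4.3 have adverse events coded in MedDRA.

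**Analysis.** Protocol 9.9.3 has: "The occurrence of pIMD(s) will be collected and summarized through the entire follow-up period in all enrolled subjects". SAP 5.4.2 has: "The occurrence of pIMD(s) will be collected and summarized through the entire follow-up period in all exposed subjects". Both then give the percentage of subjects with an exact 95% CI. SAP section 9, the place for study-specific derivation rules, is marked not applicable.

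**Oversight.** Protocol 11.3 says that "medically-attended AEFIs, serious AEFIs, pIMDs and pregnancies will be reviewed on a continuous basis by GSK safety physicians". SAP 5.2.1 lists failure to report adverse events of special interest among the important protocol deviations that do not lead to elimination.

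**The concern.** The endpoint is defined by a list of diseases, and the data are coded in a dictionary that can be searched for them. The analysis text nevertheless takes whatever was collected as a pIMD and describes no route to that status other than the investigator's recognition. A facial palsy seen in the 30 days after a dose could be recorded as a medically attended AEFI. A hospitalised Guillain-Barré case could be recorded as a serious AEFI. Both would carry a MedDRA code, yet nothing in the SAP ensures that either reaches the pIMD count. Two programmers could reach different counts in good faith, one from what sites identified and one from a term search.

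The licence approval letter cited in Protocol 7.1 asked for information on immune-mediated diseases, so this is an endpoint that the regulator wants. With few cases expected, one misplaced case matters.

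**Working it through.** **1. Reproducing the plan's own figures.** The documents give no precision figure for pIMDs. Protocol Tables 4 and 5 give exact intervals for 3000 subjects, and SAP 10.1.5.1 names Clopper-Pearson. The limits are the 2.5% quantile of Beta(x, n − x + 1) and the 97.5% quantile of Beta(x + 1, n − x). All eight distinct intervals reproduce to two decimals; for example, 15/3000 gives 0.28% to 0.82%. The same method is used below.

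**2. Expected cases.** Inputs are N = 3000 (Protocol 9.5.1), follow-up of 18 to 24 months (Protocol 9.1), and a background incidence generally below 40 per 100,000 (Protocol 9.12). The yearly time unit is an assumption, as is the lower rate of 10, which is included to show a range.

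Expected count = N × rate × years.

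| Rate per 100,000 per year | 18 months | 24 months |
|---|---|---|
| 40 | 3000 × 0.0004 × 1.5 = 1.8 | 3000 × 0.0004 × 2 = 2.4 |
| 10 | 3000 × 0.0001 × 1.5 = 0.45 | 3000 × 0.0001 × 2 = 0.6 |

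These counts are for all pIMDs together if the figure is pooled. If it is per disease, they apply to each disease, and the pooled count would be larger by an amount that the documents do not allow one to calculate.

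**3. Effect of recovering one case.**

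| Count before | Percentage (95% CI) | Count after | Percentage (95% CI) |
|---|---|---|---|
| 0 | 0% (0 to 0.123) | 1 | 0.033% (0.0008 to 0.186) |
| 2 | 0.067% (0.008 to 0.241) | 3 | 0.100% (0.021 to 0.292) |
| 5 | 0.167% (0.054 to 0.389) | 6 | 0.200% (0.073 to 0.435) |

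From 2 to 3 cases the estimate rises by half; from 5 to 6 it rises by a fifth.

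**4. Chance that at least one case is unrecognised.** With T expected cases and a proportion s recognised, the chance is 1 − exp(−T(1 − s)). No value of s is given in the documents, so a range is shown.

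| s (assumed) | T = 1.8 | T = 2.4 |
|---|---|---|
| 0.90 | 17% | 21% |
| 0.75 | 36% | 45% |
| 0.50 | 59% | 70% |

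**5. What a search could reach.** Medically attended AEFIs are recorded for 30 days after each dose, so 90 days over three doses. That is 90/548 = 16% of an 18-month follow-up and 90/730 = 12% of a 24-month one. Serious AEFIs are recorded throughout. A search therefore covers serious events over the whole follow-up, but non-serious ones only in that 12% to 16% of the time. The chances in step 4 cover all unrecognised cases, so they overstate what a search would recover.

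**The case against.** The strongest reply is that the documents contain no exclusion. Under Protocol 9.3.1.4 a listed disease is a pIMD by definition, whichever form it was entered on. The 11.1.1 wording governs when events go promptly to the sponsor, not membership of the analysis. Table 6 puts serious AEFIs and pIMDs on the same expedited AEFI screen and does not describe how a pIMD is marked there. Sponsor physicians review all these events, eCRF inconsistencies can be corrected (Protocol 9.6), and under-reporting is already a named deviation. Both example cases would be visible in the report, since medically attended AEFIs are tabulated by preferred term and serious AEFIs are listed. A selection rule could also sit in the separate table specifications (SAP 10.2), which were not available. Finally, the study is descriptive, and Protocol 9.12 already says it is limited for rare events.

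Much of this stands. A reader might infer that a pIMD counts only if the site recognises it and that listed diseases recorded elsewhere are excluded. That would be reading a rule into silence.

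The reply does not close the gap. If the definition makes a listed disease a pIMD wherever it was entered, the analysis needs a step that finds it, and none is written. The stated purpose of the physician review is real-time safety information, and no effect on the endpoint is described. The deviation category records a reporting failure without saying that the event then enters the count. The protocol does write a rule for a comparable overlap: under 9.3.1.2, a medically attended AEFI that meets a seriousness criterion is reported as serious. The rule that identifies an endpoint belongs in the SAP.

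**Conclusion.** The point holds as a possible loss of cases, not as a stated exclusion. The described route into the pIMD endpoint runs through the investigator, and the coded AEFIs are not checked against Table 3.

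The size rests on an assumed yearly reading of the Protocol 9.12 figure. At 40 per 100,000 that means about 1.8 to 2.4 expected cases, and one recovered case would change the reported percentage materially, although the intervals before and after overlap heavily. A reader might take 1.8 as a maximum. It is not: the longer follow-up gives 2.4, the source figure is qualified as general, and it refers to adolescent girls and young women while the study enrols up to age 45. If the figure is per disease, the pooled count is larger and one case weighs less.

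Nor do the documents support a claim about the net direction of error. A listed disease that is not counted lowers the figure, events identified by sites but not on the list could raise it, and no misclassification rate is given for either. The change is worth making because it is cheap and uses data already coded.

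**What to change.** In SAP 5.4.2, before the final freeze:

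1. Convert Protocol Table 3 to a fixed list of MedDRA preferred terms.
2. Run the list over all coded medically attended and serious AEFIs, and query every hit not recorded as a pIMD.
3. Report the pIMD percentage with its exact 95% CI after query resolution, beside the investigator-identified count.
4. Review investigator-identified events that are not on the list against the definition in Protocol 9.3.1.4. Do not remove them automatically, because that could narrow the definition.
5. State the limit: non-serious events after Day 30 that were never recorded cannot be recovered in this way.

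The cost is one term list, a short program and a few queries, with no extra visits. The SAP is dated 4 November 2020 and Protocol section 6 planned the end of data collection for the first quarter of 2021, so on those dates there was time.
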